6.5.1 Treatment Beyond Progression

Patients with disease progression may continue to receive the combination of tarloxotinib and sotorasib if, in the opinion of the Treating Investigator, the patient is still benefiting (e.g., asymptomatic systemic progression or local symptomatic progression) following discussion with and approval by the Principal Investigator. In addition, the following criteria must be met:

- Absence of clinical symptoms or signs indicating clinically significant disease progression
- No decline in performance status
- Absence of rapid disease progression or threat to vital organs or critical anatomical sites (e.g., CNS metastasis, respiratory failure due to tumor compression, spinal cord compression) requiring urgent alternative medical intervention

The IRB/IEC will be notified of any planned treatment beyond progression. Patients may receive palliative radiation to disease sites of progression, including brain metastases, following discussion with and approval by the Principal Investigator.

6.5.2 Tarloxotinib Dose Modifications

All patients will receive a weekly tarloxotinib infusion at the RP2Dc determined in the safety lead-in portion of the trial administered as a weekly 1-hour IV infusion on Days 1, 8, 15, and

22 of each 28-day cycle until disease progression or unacceptable toxicity. All patients will begin study treatment based on the body weight measured on Day 1 of each cycle (or within 7 days prior [e.g., Day 22 of the prior cycle]). As described above, tarloxotinib dose calculations do not need to be adjusted within a cycle unless the patient has a > 10% change in body weight. Other dose modifications may be required based on QTc prolongation, infusion-related reactions, and other tarloxotinib-related toxicity as described below.

Dose level reductions will be in a step-wise fashion. If a patient requires more than 2 dose level reductions, tarloxotinib will be permanently discontinued.

Hematologic toxicity has not been associated with tarloxotinib administration to date. However, if Grade 3 or 4 neutropenia or thrombocytopenia considered related to tarloxotinib occurs, then the treatment guidelines for non-hematologic toxicity should be followed. Dose modifications for anemia (any grade) or for Grade 2 or less neutropenia or thrombocytopenia are not required.

If a tarloxotinib-related toxicity results in a treatment delay of more than 3 weeks (withholding more than 2 doses of tarloxotinib), patients will be removed from study treatment unless otherwise approved by the Principal Investigator.

Should a dose reduction for sotorasib be required, given the potential for overlapping toxicities and challenges in attributing toxicities to one drug in a combination therapy, a dose reduction in tarloxotinib should also be considered.

Dose level	Sotorasib	Tarloxitinib
0 (full dose)	960 mg PO daily	150 mg/m ² IV weekly
-1	480 mg PO daily	100 mg/m ² IV weekly
-2	240 mg PO daily	75 mg/m ² IV weekly

6.5.3 Treatment Guidelines for QTc Prolongation

Immediate medical management of patients will be based on the following:

- a. Baseline: A pre-infusion (baseline) ECG will be obtained on all patients, if the automated measurements indicate a QTcF of ≥ 450 msec
- b. The single QTcF will be verified by manually measuring at least 3 complexes within the ECG and determining the average QTcF
- c. All patients must have a pre-infusion QTcF of < 450 msec by either: Calculation using the automated measurements of the first ECG or the manual measurement of a single ECG
- d. If it is determined that the manually read QTcF ≥ 450 msec, the Principal Investigator should be contacted to discuss the clinical significance of the reading and to determine if it is appropriate to move forward with the infusion.
- e. During treatment: Grade 3 QTc prolongation (any QTcF that is ≥ 501 msec OR > 60 msec QTcF increase relative to pre-infusion) will be manually verified by measuring at least 3 complexes with the ECG and determining the average QTcF. If QTcF prolongation is \geq Grade 3, an ECG may need to be repeated more frequently

during a patient's visit, depending on the degree of the prolongation, as indicated in this section and per institutional standards.

Note: Dose modification will be based on the average QTcF using the manual measurements.

- f. If the Investigator has any question regarding the local automated reading, a local cardiologist should be consulted. Treatment guidelines for patients experiencing QTc prolongations are provided in this section below.
- g. Patients who experience \geq Grade 3 QTc prolongation must be assessed by the Investigator (or qualified designee) prior to discharge.

6.5.4 Treatment Guidelines for QTc Prolongation

QTc Prolongation	After Tarloxitinib Administration
Grade 1 450 to 480 msec QTcF	
 • Cycle 1 and Cycle 2 Day 1 
 ◦ May be discharged if the 4-hour (or later) post-infusion QTcF is Grade 1 or lower and asymptomatic • After Cycle 2 Day 1 
 ◦ Obtain pre-infusion and 2-hour post-infusion ECGs ◦ May be discharged if the 2-hour (or later) post-infusion QTcF is \leq Grade 1 and the patient is asymptomatic • Continue the same tarloxitinib dose for subsequent cycles
Grade 2 481 to 500 msec QTcF	
 • Cycle 1 and Cycle 2 Day 1 
 ◦ May be discharged if the 4-hour (or later) post-infusion QTcF is \leq Grade 2 and the patient is asymptomatic • After Cycle 2 Day 1 
 ◦ Obtain pre-infusion and 2-hour post-infusions ECGs ◦ May be discharged if the 2-hour or later post-infusion QTcF is \leq Grade 2 and the patient is asymptomatic • Continue the same tarloxitinib dose for subsequent cycles

Grade 3 ≥ 501 msec QTcF	
 Obtain ECGs every 15 to 30 minutes until QTcF is \leq Grade 2 and then obtain ECGs every 1 hour May be discharged home if 2 subsequent measurements (at least 15 minutes apart) after the 4-hour post-infusion QTcF is \leq Grade 2 and no significant arrhythmias 
 If QTcF is ≥ 601 msec, permanently discontinue tarloxitinib If QTcF ≥ 501 msec and ≤ 600 msec 
 Resume tarloxitinib dosing with dose reduction 
 1st occurrence: reduce to 100 mg/m² 2nd occurrence: reduce to 75 mg/m² 3rd occurrence: permanently discontinue tarloxitinib Obtain ECGs prior to and hourly (for at least 4 hours) following the next tarloxitinib infusion
Grade 3 > 60 msec increase from pre-infusion QTcF AND ≤ 500 msec QTcF	
 Obtain ECGs every 15-30 minutes until QTcF is \leq Grade 2 and then obtain ECGs every 1 hour May be discharged home if 2 subsequent measurements (at least 15 minutes apart) after the 4-hour post-infusion QTcF is \leq Grade 2 and no significant arrhythmias 
 Obtain ECGs prior to and hourly (for at least 4 hours) following the next tarloxitinib infusion
Grade 4 TdP or polymorphic ventricular tachycardia, signs/symptoms of serious arrhythmia	
 Place patient on telemetry and obtain ECGs as clinical indicated Obtain Cardiologist consult and admit to hospital for extended observation on telemetry Permanently discontinue tarloxitinib

ECG = electrocardiogram; msec = millisecond; QTcF = corrected QT interval as calculated according to Fridericia's formula; TdP = Torsade de Pointes

Note: If QTcF prolongation is \geq Grade 3, an ECG may need to be repeated more frequently during the patient's visit depending on the degree of the prolongation and per institutional standards.

Treatment and retreatment guidelines in this study are based on absolute QTcF observations that vary from the NCI CTCAE. Importantly, dose reductions are not based on the QTcF change from baseline, only the absolute QTcF. For example, if a patient has a change > 60 msec from baseline but has an absolute QTcF ≤ 500 msec, no dose reduction is required.

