6.5 TREATMENT AND RETREATMENT CRITERIA

The results of tumor assessments are not required for the initiation of subsequent cycles, but patients must meet the following criteria before receiving each tarloxotinib infusion. **Note:** all ECG dose modifications will be based on the average manually measured QTcF.

- No QTcF of \geq 601 msec during any previous infusion

Note: Patients with QTcF of \geq 501 msec and $<$ 601 msec during or following the prior infusion MUST be dose reduced. If QTcF prolongation is \geq Grade 3, an ECG may need to be repeated more frequently during a patient's visit as clinically indicated, depending on the degree of the prolongation and per institutional standards.

- Check serum electrolytes
 - Pre-infusion magnesium and calcium in normal range, unless an exception is approved by the Principal Investigator.
 - If other electrolytes (e.g., sodium, chloride) are outside of the normal range, patient can receive tarloxotinib infusion if it is deemed safe per Investigator discretion.
 - Pre-infusion serum potassium must be \geq 3.5 mEq/L.
- Pre-infusion ECG: No evidence of second- or third-degree atrioventricular block
 - QTcF interval of $<$ 450 msec
- Skin rash of \leq Grade 2
- Gastrointestinal toxicity of \leq Grade 2
- Any other clinically significant tarloxotinib-related toxicity must return to at least Grade 2.

All patients not meeting retreatment criteria must be discussed with the Principal Investigator and possible dose/schedule modification and/or study treatment discontinuation discussed.

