9.2 STUDY CALENDAR

SCHEDULE OF EVENTS ⁸	SCR	C1 D1	C1 D8	C1 D15	C1 D22	C2 D1	C2 D8	C2 D15	C2 D22	C3+ D1	C3+ D8	C3+ D15	C3+ D22	EOT ⁹	SFU ⁶	LTFU
Informed consent	X															
Eligibility review	X															
Medical History	X															
Physical Exam	X	X				X				X				X	X	
ECOG Performance Status	X	X				X				X				X	X	
Vital signs ⁹	X													X	X	
Pre-infusion 30, 60, and 90 mins after EOI		X	X	X	X	X	X	X	X	X	X	X	X			
ECG 12-lead	X													X	X	
Pre-infusion EOI		X	X	X	X	X	X	X	X	X	X	X	X			
1h after EOI ¹¹		X	X	X	X	X	X	X	X	X	X	X	X			
2h after EOI ¹¹		X	X	X	X	X	X	X	X	X	X	X	X			
3h after EOI ¹¹		X	X	X	X	X	X	X	X	X	X	X	X			
4h after EOI ¹¹		X	X	X	X	X	X	X	X	X	X	X	X			
CBCD	X	X				X				X				X	X	
CMP ¹⁰	X	X	X	X	X	X	X	X	X	X	X	X	X	X	X	
Magnesium	X	X	X	X	X	X	X	X	X	X	X	X	X	X	X	
Phosphorous	X	X	X	X	X	X	X	X	X	X	X	X	X	X	X	
Serum potassium																
EOI		X				X										
3h post EOI		X				X										
Urinalysis	X															
B-HCG ²	X	X				X								X		
Biomarker samples/ctDNA samples ³		X				X								X		
Potassium Supplementation ⁴		X	X	X	X	X	X	X	X	X	X	X	X			
Tarloxotinib infusion	X	X	X	X	X	X	X	X	X	X	X	X	X			
Sotorasib dosing																
Tumor Assessment ⁵	X															
Concomitant Meds																
Adverse Events Assessment																
Survival status																X

Continuous dosing

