10.3 SAFETY ENDPOINTS

Primary safety endpoints are Dose-limiting toxicities, treatment-emergent adverse events, clinically significant changes in vital signs, electrocardiograms (especially QT), laboratory parameters (hematology, serum chemistry, urinalysis, serum pregnancy test), physical examination results.

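### After Cycle 2 Day 1 the study calendar and the QTc table give different ECG schedules, so detection of QTcF of 501 msec or more depends on which one a site follows

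*Combined protocol and SAP*

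**What the plan says.** **Study calendar (9.2).** The 12-lead ECG rows are marked in all 12 infusion columns, from Cycle 1 Day 1 to Day 22 of Cycle 3 and later. The first label reads "Pre-infusion EOI" in the extracted text, apparently two time points run together. Rows for 1, 2, 3 and 4 hours after end of infusion (EOI) follow. The ECG footnote that can be read adds tracings for Grade 3 prolongation and relaxes nothing.

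**QTc table (6.5.4).** For Cycle 1 and Cycle 2 Day 1, the Grade 1 and Grade 2 rows set discharge from 4 hours: "May be discharged if the 4-hour (or later) post-infusion QTcF is" Grade 1 or lower, or Grade 2 or lower, according to the row. After Cycle 2 Day 1 the Grade 1 row says "Obtain pre-infusion and 2-hour post-infusion ECGs" and the Grade 2 row "Obtain pre-infusion and 2-hour post-infusions ECGs". Discharge then moves to 2 hours. In the Grade 1 row: "May be discharged if the 2-hour (or later) post-infusion QTcF is" Grade 1 or lower and there are no symptoms. The Grade 3 rows add tracings, including at the following visit: "Obtain ECGs prior to and hourly (for at least 4 hours) following the next tarloxitinib infusion".

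**Missed doses (7.1.6).** If the Cycle 2 Day 1 dose is missed, that visit's assessments move to Cycle 2 Day 8, and ECGs are the example given.

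**Rules and endpoint that use the readings.** Section 6.5 says that patients with QTcF from 501 to below 601 msec "during or following the prior infusion MUST be dose reduced", and it bars further infusion after a value of 601 msec or more. Section 6.5.4 makes that a permanent discontinuation. Section 10.3 places ECG changes, with QT singled out, among the primary safety endpoints.

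**The concern.** For infusions after Cycle 2 Day 1, a site can find support in the protocol for ECG follow-up to 4 hours or for a single post-infusion tracing at 2 hours. The protocol does not say which section takes precedence.

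This affects more than visit logistics. The dose-reduction and discontinuation rules are triggered by a recorded QTcF, and so is the Grade 3 QTc count reported for a primary safety endpoint. If the number of readings varies by site, or with a patient's earlier QTc result, the chance of recording a value of 501 msec or more varies too. Maximum QTcF and Grade 3 frequency would then not be ascertained equally across patients.

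**Working it through.** The plan states no figure to reproduce. The check sets the sections side by side and counts ECGs per infusion after Cycle 2 Day 1.

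**Step 1. Where the sections agree and where they part.**

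| Period | Calendar (9.2) | Grade 1-2 rows (6.5.4) |
|---|---|---|
| Cycle 1 and Cycle 2 Day 1 | Last ECG 4 h after EOI | Discharge from the 4-hour reading |
| After Cycle 2 Day 1 | Last ECG 4 h after EOI | ECGs pre-infusion and at 2 h; discharge from the 2-hour reading |

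They agree for the first period and differ for the second. Section 7.1.6 fits a lighter schedule after Cycle 2 Day 1: there would be no need to move ECGs to Day 8 if Day 8 already had the same set. The calendar marks the two visits identically.

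**Step 2. ECGs per infusion.**

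- Calendar: pre, EOI, 1, 2, 3, 4 h = 6, of which 5 are at or after EOI.
- Table read only as a discharge rule on top of the calendar, patient leaves at 2 h: pre, EOI, 1, 2 h = 4. Lost: 3 and 4 h.
- Table read as the full schedule: pre, 2 h = 2. Lost: EOI, 1, 3 and 4 h.

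Over a cycle of four infusions: 4 × 6 = 24, 4 × 4 = 16 and 4 × 2 = 8. The last two assume that the Grade 1-2 rows apply at each of the four infusions. The table does not say whether an earlier Grade 1 or 2 reading carries forward.

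**Step 3. Direction of the error.** Both shorter sets are subsets of the calendar set, and the highest value in a subset cannot exceed the highest value in the full set. Dropping time points can therefore lower the recorded maximum QTcF or leave it unchanged, but cannot raise it. The documents do not give the time of peak QTcF after infusion, so the size of the loss cannot be calculated.

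**Step 4. Who is affected.** Table 3.1.7 gives QTc prolongation on tarloxotinib monotherapy (n = 23) as 60.9% any grade and 34.8% high grade.

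- Counts: 0.609 × 23 = 14 and 0.348 × 23 = 8.
- Worst grade 1 or 2: 60.9% − 34.8% = 26.1%, or 14 − 8 = 6 of 23.
- Applied to the 12 expansion patients: 0.261 × 12 = 3.1, about 3.

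This takes the high-grade column to mean Grade 3 or higher. Its printed heading, read literally, is above Grade 3; the 26.1% would then include Grade 3 patients and be an upper limit for worst grade 1-2. Patients whose worst grade is 3 may also have Grade 1-2 readings at other visits, which this figure does not count.

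**The case against.** **The sections can be reconciled in practice.** A reader might infer that a site cannot comply with both. That goes too far. The table does not say that the two ECGs are the only ones, and discharge is permitted, not required, on the 2-hour or a later reading. A site that takes all six calendar ECGs and discharges at 4 hours satisfies both. This stands. What remains is that a site using the permission at 2 hours cannot complete the calendar.

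**The table may describe a general 2-hour schedule, with the calendar over-marked.** A reader might infer that patients who have shown prolongation are deliberately given fewer ECGs than those who have not. That follows only if the calendar governs patients without prolongation, for whom the table has no row, while the table governs Grade 1-2 patients. Several points suggest that this was not intended. The Grade 1 discharge test is also met by a patient with no prolongation. The Grade 3 instruction for hourly ECGs at the next infusion would be largely redundant if everyone already had them. Section 7.1.6 suggests a lighter schedule for all patients after Cycle 2 Day 1. The inversion is therefore conditional, and the documents do not settle it.

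**The calendar may carry a qualifier that cannot be read.** The 1- to 4-hour rows bear a marker that reads as 11, while the legible footnotes end at 10. It may be a misread 1, which would tie those rows to the Grade 3 note, or it may point to a lost note. This stands as a limit on the finding.

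**The consequence is bounded.** Grade 3 patients receive more ECGs, not fewer. The DLT observation period in 11.1.2 is Cycle 1, where the sections agree, so lead-in DLT evaluation is not touched. Safety reporting is descriptive and single-arm. All of this stands.

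**Conclusion.** The inconsistency holds for infusions after Cycle 2 Day 1. The calendar gives 6 ECGs per infusion; the Grade 1-2 rows of 6.5.4 lead to 4 or 2, depending on how they are read, once a patient is discharged at 2 hours. Detection of QTcF of 501 msec or more, and with it mandatory dose reduction, discontinuation and the reported Grade 3 QTc frequency, then depends on which section a site follows. The error can only run towards missed values, by an amount that the documents do not allow one to estimate.

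Two larger claims are not supported. A reader might take the 60.9% any-grade rate as the share with reduced monitoring. It includes the 34.8% with high-grade prolongation, who fall under rows that add ECGs (if that column means Grade 3 or higher); about 26% is the better guide to patients with a worst grade in the affected rows. A reader might also take 2 ECGs against 6 as the established difference, but that is the extreme reading and 4 against 6 is equally open.

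The conclusion assumes that no unreadable calendar footnote already limits the 1- to 4-hour rows in later cycles. It takes no position on which monitoring schedule is right.

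**What to change.** Reconcile 6.5.4, 7.1.6 and 9.2 so that one ECG schedule and one discharge time after Cycle 2 Day 1 are stated in all three places. The sponsor's clinicians should choose that schedule and say explicitly which patients it covers. Check the marker that reads as 11 on the 1- to 4-hour calendar rows against the source PDF, and restore or correct its footnote.

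If the number of ECGs will still differ between patients, add to 11.2.4 that Grade 3 QTcF is reported on the time points common to all patients, alongside the result from all time points. If one schedule applies to everyone, this addition is largely unnecessary.

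The cost is a wording amendment and, in the second case, a little extra analysis. Keeping the calendar schedule adds no procedure beyond those it already marks; keeping the shorter one means fewer.

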6.5.5 Treatment Guidelines for Infusion-related Reactions

Treatment and management of infusion-related reactions will be based on the severity and type of symptom(s) experienced. Treatment guidelines for infusion-related reactions are presented in the table below.

Grade (CTCAE v5.0)	Definition	Treatment Guideline
Grade 1	
 • Mild transient reaction • Infusion interruption not indicated • Intervention not indicated 	
 • Monitor for at least 2 hours after the end of the infusion • Provide patient instructions and prophylactic medications at discharge as appropriate • Consider adjusting premedication based on symptoms for subsequent infusions
Grade 2	
 • Therapy or infusion interruption indicated but responds promptly to symptomatic treatment • Prophylactic medications indicated for ≤ 24 hours 	
 • Interrupt tarloxitinib infusion • Administration of medications (e.g., anti-histamines, steroids, NSAIDs and IV fluids), as appropriate • Monitor for at least 2 hours after the end of the infusion • Consider adjusting premedication based on symptoms for subsequent infusions • After symptoms resolve to baseline, resume future tarloxitinib infusions to 50% of the initial infusion rate

Grade 3	
 • Prolonged (e.g., not rapidly responsive to symptomatic medication and/or brief interruption of infusion) • Recurrence of symptoms following initial improvement, hospitalization indicated for clinical sequelae 	
 • Interrupt tarloxitinib infusion • Administration of medications (e.g., anti-histamines, steroids, NSAIDs and IV fluids), as appropriate • Hospitalization for medical care and observation • Reduce tarloxitinib dose to 120 mg/m² for subsequent doses*, and/or adjusted premedication after discussion with the Principal Investigator • If Grade 3 infusion reaction recurs after this initial dose reduction, then reduce the tarloxitinib dose to 75 mg/m² for subsequent doses • After symptoms resolve to baseline, resume future tarloxitinib infusions to 50% of the initial infusion rate
Grade 4	
 • Life-threatening consequences • Urgent intervention indicated 	
 • Hospitalization for urgent medical treatment • Discontinue tarloxitinib permanently

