6.5.6 Treatment Guidelines for Other Non-Hematologic Toxicity

The table below provides treatment guidelines for treating tarloxitinib non-hematologic toxicities other than QT prolongation and infusion-related reactions.

Toxicity (CTCAE v5.0)	Details	Hold Dose	Dose Levels After Recovery to \leq Grade 2 or Baseline
Grade 2	Intolerable skin toxicity or diarrhea	Hold dose until resolution to Grade 0 or 1 or Grade 2 tolerable	If symptoms are intolerable, recurrent, or not controlled by supportive care, hold dose until symptoms improve and reduce to next lower dose level
Grade 2	ALT or AST $> 3 \times$ ULN	Hold dose until resolution to $<$ Grade 2 or baseline	150 mg/m ² (no reduction)
	ALT or AST $> 3 \times$ ULN (Grade 2) AND a total bilirubin $\geq 2 \times$ ULN (patients without liver metastasis)**	Treatment to be discontinued	Not applicable
Grade 3	Nausea and vomiting*	Hold dose until resolution to Grade 0 or 1 or Grade 2 tolerable	120 mg/m ² ; if recurs, then second reduction to 75 mg/m ²
Grade 4	Pulmonary embolism that is adequately treated	Hold dose until resolution to Grade 0 or 1	120 mg/m ² ; if recurs, then second reduction to 75 mg/m ²
Grade 4	All other life-threatening conditions	Treatment to be discontinued	Not applicable

ALT = alanine aminotransferase; ASP = aspartate aminotransferase; CTCAE = Common Terminology Criteria for Adverse Events; ULN = upper limit of normal

* May hold or reduce if nausea/vomiting continues despite optimized anti-emetic treatment

** Tarloxitinib-related toxicity meeting the definition of Hy's Law, tarloxitinib will be discontinued permanently

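### Tarloxotinib reductions are printed as absolute doses: taken together, the first steps are all reductions only from 150 mg/m², although patients may start at 100 or 75 or may already have been reduced

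*Combined protocol and SAP*

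**What the plan says.** **Starting dose.** Under Section 6.5.2, patients receive the combination dose chosen in the lead-in. Section 11.1 starts at 150 mg/m² and enrols at the next level down if 150 fails, so patients may start at 100 or 75. The dose-level tables in Section 1, Section 6.1 and Section 6.5.2 list 150, 100 and 75 only.

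**QTc.** Section 6.5 says that patients with QTcF from 501 to below 601 msec "during or following the prior infusion MUST be dose reduced". Section 6.5.4 says "Resume tarloxitinib dosing with dose reduction" and prints the doses: "1st occurrence: reduce to 100 mg/m²", then "2nd occurrence: reduce to 75 mg/m²". A third occurrence stops the drug.

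**Other toxicities.** For a Grade 3 infusion reaction, Section 6.5.5 says "Reduce tarloxitinib dose to 120 mg/m² for subsequent doses". It gives 75 as the next dose, under the condition "If Grade 3 infusion reaction recurs after this initial dose reduction". Section 6.5.6 prints 120 for Grade 3 nausea and vomiting and for treated Grade 4 pulmonary embolism: "if recurs, then second reduction to 75 mg/m ²". For Grade 2 ALT or AST elevation it prints 150, labelled as no reduction.

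**Relative wording already in use.** The row in Section 6.5.6 for intolerable Grade 2 skin toxicity or diarrhea says "hold dose until symptoms improve and reduce to next lower dose level".

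**General rule.** Section 6.5.2 says that reductions are step-wise down the 150/100/75 ladder, and that a patient who needs more than two stops tarloxotinib.

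**The concern.** The starting dose can vary and the printed reduction doses do not. A step that is a reduction for a patient on 150 can leave a patient on a lower dose unchanged, or name a higher dose. The QTc row matters most, because reduction there is mandatory and QTc prolongation is tarloxotinib's most frequent high-grade event in the Section 3.1.7 table (34.8% of 23 patients). Where the table and the general rule give different doses, each investigator has to choose, and similar patients may be treated differently. The stakes are patient safety and consistent dosing.

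**Working it through.** The plan gives no figure of its own to reproduce. The check compares each printed dose with each dose a patient may currently be on.

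**Inputs.** Printed steps: 100 then 75 (6.5.4); 120 then 75 (6.5.5, 6.5.6); 150 after Grade 2 ALT/AST elevation (6.5.6). Current doses: 150, 100 and 75 (dose-level tables), and 120 (a patient already cut under 6.5.5 or 6.5.6).

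**Formula.** Change = printed dose / current dose − 1. For example, 100/75 − 1 = +33% and 120/100 − 1 = +20%.

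| Printed step | on 150 | on 120 | on 100 | on 75 |
|---|---|---|---|---|
| QTc, first: 100 | −33% | −17% | 0% | +33% |
| QTc, second: 75 | −50% | −37.5% | −25% | 0% |
| Infusion reaction, nausea/vomiting, embolism, first: 120 | −20% | 0% | +20% | +60% |
| Same three, second: 75 | −50% | −37.5% | −25% | 0% |
| Grade 2 ALT/AST, resume: 150 | 0% | +25% | +50% | +100% |

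The ALT/AST row is meant to leave the dose unchanged, and it does so only from 150.

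**Count by starting dose.** Four triggers with two printed doses each give 8 steps. Steps that do not lower the starting dose: 0 of 8 from 150; 4 of 8 from 100 (the first QTc step and the three 120 steps); 8 of 8 from 75.

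**Start at 150, first occurrences of two different triggers.** There are 4 × 3 = 12 ordered pairs.
- QTc, then a 120 row: 3 pairs, 100 to 120, +20%.
- One 120 row, then another: 6 pairs, 120 to 120, 0%, because recurrence is naturally read as the same toxicity returning.
- A 120 row, then QTc: 3 pairs, 120 to 100, −17%.

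So 9 of the 12 give no reduction at the second event. Both counts are unweighted lists of what the tables print. They are not frequencies.

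**Set against the ladder in 6.5.2.** From 100, the step-wise rule implies 75, while the QTc table says 100 and the other rows say 120. From 75, the ladder has no lower level. The two-reduction cap covers a patient who started at 150 and has been reduced twice. It does not cover a patient who started at 75, or who started at 100 and has been reduced once.

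**How often lower starts might arise (illustration only).** The documents give no DLT rate for the combination, so assume a true rate p. A level passes if at most 1 of 6 patients has a DLT: pass = (1−p)^6 + 6p(1−p)^5.
- p = 10%: pass 0.886, so 150 fails with probability 11%.
- p = 20%: pass 0.655, fails 34%.
- p = 30%: pass 0.420, fails 58%.

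If the same rate also held at 100, both levels would fail, and patients would be enrolled at 75, with probability 0.114² = 1%, 0.345² = 12% and 0.580² = 34%.

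**The case against.** The strongest reply is that Section 6.5.2 already settles the matter. Reductions are step-wise, the ladder is printed, and Section 6.5 insists on a reduction, so a patient on 100 goes to 75. This stands in part: it would be wrong to say that the plan offers no lower dose to a patient on 100. But the specific tables print something different, nothing says which governs, and the ladder gives no action for a patient at 75 with fewer than two reductions.

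Second, two of the four triggers do not force a reduction. The infusion-reaction row allows adjusted premedication instead, after discussion with the Principal Investigator, and the footnote on nausea and vomiting makes holding or reducing optional. That is correct and is why the counts above must not be read as rates. The QTc row has no such alternative.

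Third, a reader might infer that the tables work only for a patient on 150. They do not go that far: the QTc step still reduces from 120, every second step to 75 reduces from 100 and 120, and the skin and diarrhea row is already relative. It is the first steps, taken together, that all reduce only from 150.

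Fourth, the 34.8% in Section 3.1.7 is not the trigger rate. Section 6.5.3 counts a rise of more than 60 msec as Grade 3, whereas Section 6.5.4 requires no reduction when such a rise leaves QTcF at 500 msec or below. The documents do not split the figure.

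Doses below 75 are left out of the argument. Section 11.1 leaves them to be determined, and the tables could be revised when they are defined.

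**Conclusion.** The point holds. In a scenario that the plan provides for, a mandatory QTc reduction is printed as a dose that is unchanged from 100 and 33% higher than 75, and the second step is unchanged from 75. The 120 mg/m² step belongs to no dose-level table and exceeds 100 by 20% and 75 by 60%. It also conflicts for a patient who started at 150 and was already cut to 100 for QTc. The ALT/AST entry has the same fault (+50% from 100, +100% from 75).

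A reader might infer that patients would actually be given more drug after a QTc event. The documents do not support that: the wording plainly intends a reduction, patients who fail retreatment criteria must be discussed with the Principal Investigator, and QTcF of 601 msec or more, Grade 4 QTc events and a third occurrence all stop the drug. Nor does the fault reach the rule for choosing the combination dose, the response criterion or the toxicity-monitoring boundaries.

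The comparison of doses needs no assumption beyond the printed numbers. Only the probabilities of a lower start rest on assumed DLT rates. This should be fixed because it is a safety instruction and the correction is cheap.

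**What to change.** - **6.5.4:** replace the two printed doses with a reduction to the next lower tarloxotinib dose level from the patient's current dose.
- **6.5.5 and 6.5.6:** state that 120 then 75 applies only to a patient currently on 150. Any other patient goes to the next lower level in the tarloxotinib column of the 6.5.2 table. From 120 this means 100 for a different toxicity; recurrence of the same toxicity stays at 75, as now printed.
- **All three tables:** when a reduction is required, never resume at or above the current dose. A patient at the lowest level who needs a further reduction discontinues tarloxotinib.
- **ALT/AST row in 6.5.6:** replace the fixed 150 with an instruction to resume at the same dose.

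Whether to keep 120 at all is a clinical decision for the sponsor: dropping it would turn a 20% first cut into a 33% cut for three toxicities. If it is kept, the amendment should say whether a cut to 120 counts towards the two-reduction cap. If it does, 150 to 120 to 100 uses both.

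**Cost:** a short amendment to three tables, with no change to sample size, decision rule or monitoring boundary. The downside is that patients who start at 100 or 75 may stop tarloxotinib sooner.
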